# > X-ray using Pettersson scale (if available)

The World Federation of Hemophilia endorsed a radiographic scale, commonly referred to as the Pettersson scale , to measure hemophilia joint health status. Eight parameters are weighted and summed to give a score for the joint as shown in. Pettersson scores of all joints will be collected during screening, intervals, and termination visits or whenever the treating physician deems it appropriate.

	Table 7 Pettersson Scale for Radiographic Evaluation of Hemophilic Joints
X-Ray	Osteoporosis:
	Absent: 0 Present: 1
	Enlarged epiphysis:
	Absent: 0 Present: 1
	Irregular subchondral surface:
	Absent: 0 Surface partially involved: 1 Surface totally involved: 2
	Narrowing of joint space:
	Absent: 0 Present with joint space <1 mm: 1 Present with joint space >1 mm: 2
	Subchondral cyst formation:
	Absent: 0 1 cyst: 1 >1 cyst: 2
	Erosion at joint margins:
	Absent: 0 Present: 1
	Gross incongruence of articulating bone ends:
	Absent: 0 Slight: 1 Pronounced: 2
	Joint deformity (angulation and/or displacement between articulating bones):
	Absent: 0 Slight: 1 Pronounced: 2
Source: Pette	ersson H et al 1980 

Source: Pettersson H et al 1980 4

- ➤ Magnetic Resonance Imaging scoring system and or ultrasound scanning (if available and used at site)
  - Several MRI scoring systems have been developed to measure hemophilia joint health status. One of the most commonly used systems was one that was developed in Lund, Sweden. MRI scores of all joints will be collected during screening, intervals, and termination visits or whenever the treating physician deems it appropriate. The scoring system  used shall be determined by the subject's radiologist.

Ultrasound evaluation of joint status is currently being studied by international groups. 48 Ultrasound can be used to identify haemarthroses and to evaluate the synovium for signs of inflammation. Inflamed synovium demonstrates increased flow with colour and power Doppler imaging and it may be seen to be thickened and nodular. Ultrasound can distinguish between haemarthrosis and synovial hypertrophy. It has the ability of differentiating synovium hypertrophy and hemosiderin deposition. 49 Ultrasound analysis of joints will be collected during screening, annual intervals, and termination visits or whenever the treating physician deems it appropriate.

Table 8  Magnetic Resonance Imaging Scoring System Developed in Lund, Sweden				
Subchondral Cyst				
Present in at least 1 bone Present in at least 2 bones >3 cysts in at least 1 bone >3 cysts in at least 2 bones Largest size >4 mm in at least 1 bone Largest size >4 mm in at least 2 bones				
Irregularity/erosion of subchondral cortex				
Present in at least 1 bone Present in at least 2 bones Involve more than half of joint surface in at least 1 bone Involve more than half of joint surface in at least 2 bones				
Chondral destruction				
Present in at least 1 bone Present in at least 2 bones Full thickness defect in at least 1 bone Full thickness defect in at least 2 bones Full thickness defect involves >1/3 of joint surface in at least 1 bone Full thickness defect involves >1/3 of joint surface in at least 2 bones				
0 absent				
1 equivocal				
2 small				
3 moderate 4 large				

Source: Lundin B et al. 2004 44

- ➤ Number of total target joints (defined as 3 or more bleeds in the same joint in a 6 month period )
- Number of invasive surgical procedures, such as (but not exclusively orthopedic) surgery, radiosynovectomy, and chemosynovectomy per year per patient

AICC/FEIBA Page 38 of 77 Clinical Study Protocol Identifier: 091301 2017 DEC 19

## 9.3.2 Quality of Life Variables

## 9.3.2.1 Health-Related Quality of Life

QoL questionnaires will be provided at the screening visit and on an annual basis to subjects or subjects' legally authorized representatives who opt to voluntarily complete them. Some QoL questionnaires may not be available in all languages and therefore will not be available at all study sites.

- SF-12v2, and EQ-5D questionnaires for adult subjects  $\geq$  18 years
  - ➤ The SF-12v2 measures generic health-related quality of life.
  - The EQ-5D measures health utility and it is a descriptive system of health-related quality of life consisting of five dimensions: mobility, self-care, usual activities, pain/discomfort and anxiety/depression. Each dimension has 3 levels of severity: no problems, some problems, extreme problems.
- SF-10, measures generic health-related quality of life for children aged 4-13 and is parent-completed.
- EQ-5D-Y (Youth version). Descriptive system of youth health-related quality of life states consisting of five dimensions (mobility, looking after myself, doing usual activities, having pain or discomfort, feeling worried, sad or unhappy) each of which can take one of three responses. The responses record three levels of severity (no problems/some problems or a bit/a lot (of) problems or very) within a particular EQ-5D dimension. It can be parent-completed and used in children of age 7-17 50,51,52
- HemoQoLiii scale for both adults (Hem-A-QoL ≥ 18 years) and children (HemoQol) aged 4-17. The Haemo-QoL is a quality of life assessment instrument for children and adolescents with haemophilia. There are 3 sets of psychometrically tested questionnaire versions for three age groups of children as well as their parents. In addition to the full version, a short version for small children (4-7 years) containing 16 items and a short version for older children (8-16 years) containing 35 items were developed. An 8-item index version was developed spanning all age groups which is also available as a self and parent-report.

\_

ii http://www.haemoqol.de

#### 9.3.2.2 Pain

- Chronic pain (defined as "Continuous and/or intermittent pain, related to the pathophysiology of haemophilia, requiring intervention (pharmacological or non-pharmacological pain treatment), in which the cause of pain cannot be readily removed, occurring more than once a week and lasting 3 months or more")  associated with hemophilia
- Acute pain associated with bleeding episodes in haemophilia patients
   Chronic pain and acute pain associated with haemophilia will be assessed by
  - Numeric Rating Scale
    The numeric rating scale (NRS) is a unidimensional measure of pain intensity in adults. The most commonly iteration used is the 11-items NRS. The common format is a horizontal bar or line. Similar to the pain visual analogue scale (VAS), the NRS is anchored by describing pain severity extremes. It can be administered either verbally or graphically for self-completion and the subject is asked to indicate the numeric value on the segmented scale that best describes pain intensity.
  - ➤ Pediatric subjects or subjects that have difficulty quantifying their pain numerically can be asked to assess the pain by using the following Wong Baker Face Scale

Explain to the individual that each face is for an individual who feels happy because he has no pain (hurt) or sad because he has some or a lot of pain. Face 0 is very happy because he does not hurt at all. Face 1 hurts just a little bit. Face 2 hurts a little more. Face 3 hurts even more. Face 4 hurts a have let in Face 5 hurts as much as you can imagine, although the individual so not have to be crying to feel this bad. Ask the individual to choose the face that best describes how he is feeling. This rating scale is recommended for individuals 3 years and older. Brief instructions: point to each face using the words to describe the pain intensity. Ask the individual to choose the face that best describes the pain and record the appropriate number.

During the screening and on an annual basis – or more frequently based on current standard at the site - the investigators shall ask subjects to rate the average level of chronic pain associated with haemophilia over the period of 4 weeks prior to visit date using the NRS. The scores will be recorded in subject diary and the completion of the NRS will be done on a voluntary basis.

During the interval and termination visits, the investigator will determine the level of completeness in record keeping. If the investigator decides not to transcribe the data into the CRF, a comment explaining the reason needs to be provided in the corresponding section of the CRF.

## 9.3.2.3 Daily Activity Level

Daily activity level, if available, will be assessed by Haemophilia Activity Level scale (HAL)  in adults and Pediatric Haemophilia Activity Level scale (PedHAL) in children.

- The HAL measures activities involving the upper extremities, basic activities involving the lower extremities and complex activities involving the lower extremities as well as an overall physical activity score for adults.. The aim of this questionnaire is to determine the ability of the subject to perform the following activities.
  - Lying down/ sitting / kneeling / standing
  - > Functions of the legs
  - > Functions of the arms
  - ➤ Use of transportation
  - > Self-care
  - ➤ Household tasks
  - ➤ Leisure activities and sports
  - Adaptations and using an aid

There are six different response options (Impossible, always, mostly, sometimes, rarely, never).

- The pedHAL measures a number of activities involving the upper extremities, basic activities involving the lower extremities and complex activities involving the lower extremities as well as an overall physical activity score for children. The aim of this questionnaire is to determine the ability of children to perform the following activities:-
  - ➤ Sitting / kneeling / standing
  - > Legs
  - > Arms
  - ➤ Use of transportation
  - > Self-care
  - ➤ Household tasks
  - ➤ Leisure activities and sports
  - > Adaptations and using an aid

#### 9.3.3 Economic Variables

- Health resource use:
  - Number of visits at the site
  - > Unscheduled visits at the site
  - Number of hospitalizations and length of stay (number of days) related to haemophilia (surgery excluded)
  - Length of stay in hospital per inpatient hospitalization
  - Number of days lost from school or work due to bleeding episodes
  - ➤ Antiphlogistic drug use

## 9.3.4 Pharmacodynamic Variables

- Individual pharmacodynamic properties (PD) of FEIBA NF by thrombin generation assay (TGA), if available
  - TGA measures the thrombin concentrations before and after clot formation and it is very sensitive to variations in individual or groups of coagulation factors. *In vitro* spiking of high-titre inhibitor plasma with increasing concentrations of FEIBA NF resulted in the dose-dependent restoration of the thrombin-generating capacity of the FVIII-inhibitor plasma. It has been reported  that defective thrombin generation is reversed in patients with FVIII inhibitors within 30 min after a single injection of therapeutic doses of FEIBA NF. The changes in the kinetics of thrombin generation measured before, during and after FVIII-bypassing therapy reflect the pharmacological effect of the drug. TGA may enable the pharmacodynamic and pharmacokinetic properties of bypassing therapies to be monitored, thus helping to optimize treatment, however, more data on clinical efficacy in relation with TGA are needed 
  - ➤ Thrombin generation (TG) can be used to individualize FEIBA NF treatment as a component of overall coagulation monitoring for major surgeries 
  - Assessments from TGA [peak thrombin (nmol/L), ETP (area under the curve), lag time (time to start of observable thrombin generation), velocity index (nmol/L\*min) and time to thrombin generation peak (min)] will be summarized for subjects with available data. Time points of blood collection and the method used for TGA execution will be collected and analysed. Date/time of the last FEIBA infusion, total units given (U), body weight (kg) at time of infusion, pre and post-infusion blood draws), the laboratory where TGA was assessed, and reason of infusion (i.e., to assess TGA) will be recorded

The association between these parameters and bleeding rates, bleeding treatment efficacy and overall effectiveness, total dose (U/kg), and the total number of infusions for bleeding will be evaluated (treatment will be evaluated using a non-parametric Spearman's correlation coefficient, for both prophylaxis and on-demand treatment).

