# 9.2.2 Duration of Study Period and Subject Participation

The overall duration of the study is expected to be approx.7 years from the study initiation (i.e. first subject enrolled) to study completion (i.e. last subject last visit). The recruitment period is planned to be approx.3 years. The subject participation period is 4 years from enrollment to study completion (i.e. last study visit) unless prematurely discontinued for whatever reason.

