## 9.7.1.1 Calculation of Annualized Bleeding Rates (ABR)

The annualized bleeding rates (ABR) will be calculated as follows: (total number of bleeding episodes÷observed treatment period in days) \* 365.25.

The treatment period for emergency surgery will be excluded from the bleed rate calculation.

Bleeding occurring prior to the first prophylactic infusion will not be included for the estimation of bleed rate. The observation period for the on-demand regimen will commence on the day of enrollment (met all inclusion and exclusion criteria); the period for the prophylaxis arm will commence at the first prophylactic infusion once enrolled (met all inclusion and exclusion criteria).

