#### 9.7.1.2 Minimal Observed Treatment Period to Estimate ABR

For enrolled subjects that have met all inclusion and exclusion criteria, subjects who have at least 1 assessment [defined as having a minimum of 3-month (≥90 days) observational period on regimen] but do not complete the full study period of four years, the annualized bleeding rate will be estimated from the interval assessments.

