## 9.7.3.2 Methods of Analysis for Other Primary Efficacy Criteria

The annualized rate of bleeding episodes in joints, target joints, and other anatomical locations for on-demand and prophylaxis subjects will be summarized.

The frequency distribution for number of infusions for bleed treatment will be reported for each of the treatment regimens. The median number of infusions per bleeding episode for each subject will be calculated. The weight-adjusted dose (U/kg) per bleeding episode per subject will be described for on-demand and prophylaxis treatment regimens.

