## For treatment of bleeding episodes:

Corresponding to all treated (with FEIBA NF) bleeding episodes the following parameters and statistics will be computed separately by each treatment regimen (prophylaxis, on-demand):

Parameter	Statistics
Total number of subjects infused	Sum
Total exposure days	Median(Q1,Q3)
Total number of infusions	Median(Q1,Q3)
Number of unique lots used	Sum
Units administered per subject, per infusion (U)	Median(Q1,Q3)
Units administered per subject, per week (U)	Median(Q1,Q3)
Units administered per subject, per month (U)	Median(Q1,Q3)
Annualized units administered, per subject (U)	Median(Q1,Q3)
Total units administered, per subject (U)	Median(Q1,Q3)
Weight-adjusted dose per subject, per infusion (U/kg)	Median(Q1,Q3)
Weight-adjusted dose per subject, per week (U/kg)	Median(Q1,Q3)
Weight-adjusted dose per subject, per month (U/kg)	Median(Q1,Q3)
Annualized weight-adjusted dose, per subject (U/kg)	Median(Q1,Q3)
Total weight-adjusted dose, per subject (U/kg)	Median(Q1,Q3)

Total number (%) of treated bleeds and their corresponding hemostatic efficacy ratings using an "excellent-to-poor" 4-point Likert scale by the subjects or caregiver for treatments given at home or by the investigator for treatments given in the hospital/clinic.

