## 9.7.3.7 Methods of Analysis Pharmacodynamic (TGA) Endpoints

Descriptive statistics and figures will be computed by treatment regimen (on-demand, prophylaxis) to assess the pharmacodynamic responses from TGA parameters over the course of the study. Means (SD), medians (IQR), first quartile, third quartile, 95% confidence intervals of point estimates, maximum, and/or minimum will be generated. There will be no formal statistical comparison conducted. TGA parameters will include peak thrombin [nmol/l], endogenous thrombin potential (ETP, area under the curve) [nmol\*min/L], onset time (time to the start of observable thrombin generation) [minutes], and peak time (time to reach the peak thrombin) [minutes].

The association between TGA parameters and bleed rates, total dose (U/kg), and the number of infusions for bleeding treatment will be evaluated using a non-parametric Spearman's correlation coefficient by independent treatment regimens (on-demand and prophylaxis).

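### The TGA correlations use cumulative dose and cumulative bleed infusions, so they partly measure time on regimen, with a bias that can go in either direction

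*Protocol*

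**What the plan says.** Section 9.3.4 names the clinical variables to be correlated with the TGA parameters. After bleeding rates and effectiveness it lists "total dose (U/kg), and the total number of infusions for bleeding will be evaluated". Section 9.7.3.7 repeats the plan by regimen: "total dose (U/kg), and the number of infusions for bleeding treatment will be evaluated". Both specify Spearman's coefficient. Neither divides dose or infusions by time or by number of bleeds.

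The bleed rate in the same sentences is standardised for time: section 9.7.1.1 divides the bleeds by the observed days and multiplies by 365.25.

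The dose tables in section 9.7.3.2 have one row for "Annualized weight-adjusted dose, per subject (U/kg") and another for "Total weight-adjusted dose, per subject (U/kg"). On the protocol's own labels these are different quantities.

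On observation time, section 9.2.2 says: "The subject participation period is 4 years from enrollment to study completion", unless the subject discontinues early. Section 9.3.6 keeps the data of early leavers up to exit, and its reasons for leaving include disappearance of the inhibitor and success of immune tolerance induction (ITI). Section 9.7.1.2 sets a "minimum of 3-month (≥90 days) observational period on regimen", but for estimating the annualized bleeding rate (ABR).

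**The concern.** A cumulative total is a rate multiplied by the time over which it accrued. If time on regimen differs between subjects, a rank correlation with the total orders them partly by length of observation. The same holds within each regimen, because a subject who leaves early or changes regimen contributes a short segment.

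Section 7.1 lists the possible correlation between TGA and clinical outcome among the study's questions, and section 9.3.4 says that more data on it are needed. About 55 evaluable subjects are planned, TGA is recorded only if available, and results are split by regimen. There is little information to spare. A weak coefficient could be read as no relation, and a moderate one could reflect only who stayed longer.

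**Working it through.** The protocol gives no expected correlation, power or precision for this analysis, so there is no stated figure to reproduce.

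**1. How far the totals can drift.** The upper limit is 4 years = 4 × 365.25 = 1461 days (9.2.2). As an illustrative lower limit I use 90 days, borrowed from the ABR rule in 9.7.1.2. The range is 1461/90 = 16.2-fold.

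- Dose, illustrated with the crossover study's regimen cited in 7.1 (85 U/kg three times weekly, 255 U/kg per week): 255 × 90/7 = 3,279 U/kg, against 255 × 1461/7 = 53,222 U/kg.
- Bleeds, at the median ABRs cited in 7.1: 28.7 × 90/365.25 = 7.1 against 28.7 × 4 = 114.8 on demand, and 7.9 × 90/365.25 = 1.9 against 7.9 × 4 = 31.6 on prophylaxis.

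**2. Time unrelated to TGA.** Simulation with 200,000 subjects per scenario.

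- From section 7.1: between-subject CVs of 7.1/13.1 = 0.54 on demand and 5.0/5.0 = 1.0 on prophylaxis, and the two ABR levels above.
- Assumed: true Spearman of -0.50 between TGA and each subject's underlying rate, lognormal rates, Poisson counts, and a dose-rate CV of 0.15 to 0.30.
- Assumed follow-up: non-completers spread evenly from 90 days to 4 years.

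| Follow-up on one regimen | Total infusions, on demand | Total infusions, prophylaxis | Infusions per year | Total dose |
|---|---|---|---|---|
| All complete 4 years | no loss | no loss | reference | no loss |
| 80% complete | -0.42 | -0.44 | -0.48 to -0.49 | -0.36 to -0.39 |
| Half complete | -0.34 | -0.40 | -0.48 | -0.21 to -0.28 |
| Uniform, 90 days to 4 years | -0.30 | -0.38 | -0.47 | -0.13 to -0.22 |

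Annualized dose stays at about -0.50 in this model. Infusions per year fall slightly short of -0.50 because counts are noisy. Under uniform follow-up, total infusions correlate 0.57 to 0.75 with time alone, which is stronger than their correlation with TGA.

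**3. Time related to TGA.** A second run used the on-demand level of 28.7 bleeds per year, CV 0.54, about 2 infusions per bleed, and an assumed correlation of ±0.3 between time and TGA. Follow-up was half completing, uniform or log-uniform.

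- No true association: total infusions give a spurious ±0.17 to ±0.24, and infusions per year give about 0.00.
- Underlying correlation -0.5, time–TGA correlation -0.3: total infusions give -0.45 to -0.48, so no dilution shows.
- Underlying correlation -0.5, time–TGA correlation +0.3: total infusions give -0.16 to 0.00.

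**4. Which replacement for infusions.** Section 9.7.3.2 already plans a per-bleed summary: "The median number of infusions per bleeding episode for each subject will be calculated". It is undefined for a subject without bleeds, and section 7.1 reports 6 patients with no bleed during prophylaxis in the crossover study. Using it as the main correlate would drop the best responders. Infusions per year is zero for such a subject and keeps him in the ranking.

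**The case against.** **Neither section defines total.** The cumulative meaning is read from table labels elsewhere, and 9.7.3.7 drops the word before infusions. Derivations are often left to the analysis plan. This weakens the infusion half somewhat. It hardly touches the dose half, where both sections write total dose and the tables give total and annualized dose side by side. If a per-bleed or per-year quantity was meant, the wording still has to change.

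**The size rests on assumptions.** The -0.50 and the follow-up patterns are not in the protocol. The approximate sampling SD of one Spearman estimate, (1 - ρ²) × √((1 + ρ²/2)/(n - 3)) at ρ = -0.45, is 0.12 for n = 55 and 0.17 for n = 27. With 80% completing, the shift for infusions is smaller than that. This stands, although the shift is systematic and avoidable, and it is larger for dose.

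**The analysis is secondary and descriptive.** Section 9.7.3.7 rules out formal comparison, and the time-standardised bleed-rate correlation already addresses the clinical question. This stands and limits the importance of the point.

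**Three stronger readings are tempting, and the protocol does not support them.** A reader might infer that the coefficients are always pulled toward zero. That needs time on regimen to be unrelated to TGA, and the outcome-related exits in 9.3.6 mean this cannot be assumed. A reader might take 90 days as the documented lower limit, but it is stated for ABR only, so the spread here could be wider. A reader might add interim cut-offs as a source of unequal time, but 9.7.3.8 does not say that these correlations are run at interim.

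**Conclusion.** The point holds, with moderate weight. As written, two of the TGA correlates are cumulative, while the bleed rate beside them is standardised for time. Their coefficients therefore depend on time on regimen as well as on any relation with TGA.

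The effect is nil if every subject completes 4 years on one regimen, small for infusions and moderate for dose if about 80% do, and substantial if many leave or switch. Its direction is known (dilution) only if time is unrelated to TGA. These sizes rest on the assumed correlation, follow-up patterns and dose-rate spread. That the totals grow with observation time does not depend on them.

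The primary endpoint and the bleed-rate correlation are unaffected.

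**What to change.** Make the same change in sections 9.3.4 and 9.7.3.7:

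- Replace total dose with annualized weight-adjusted dose per subject. State which version is meant, because 9.7.3.2 has this row in both the bleed-treatment table and the prevention (whole-regimen) table.
- Replace the (total) number of bleed infusions with bleed infusions per year on regimen: (bleed infusions ÷ observed days on regimen) × 365.25, using the ABR observation period of 9.7.1.1. Subjects with no bleeds stay in with a value of zero.
- Optionally add median infusions per bleeding episode as a supplementary correlate, restricted to subjects with at least one treated bleed and labelled as such.
- Keep the bleed rate as it is.
- State whether the 90-day minimum of 9.7.1.2 also applies to these correlations.

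The cost is a wording change in two sections. No new data are needed: annualized dose is already planned, and infusions and observed days are already recorded. The downside is slightly noisier rates for subjects with short observation.
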